11.6.2.1 Pulmonary Events

Dyspnea, cough, fatigue, hypoxia, pneumonitis, and pulmonary infiltrates have been associated with the administration of atezolizumab.

All pulmonary events should be thoroughly evaluated, as follows, for other commonly reported etiologies such as pneumonia/infection, lymphangitic carcinomatosis, pulmonary embolism, heart failure, chronic obstructive pulmonary disease, or pulmonary hypertension. For specific management guidelines, please see table 3.

Table 3. Management Guidelines for Pulmonary Events, including pneumonitis

Adverse Event	Management
Pulmonary event, Grade 1	
Continue atezolizumab and monitor closely.Re-evaluate on serial imaging.Consider subject referral to pulmonary specialist.
Pulmonary event, Grade 2	
Withhold atezolizumab for up to 12 weeks after event onset.^aRefer subject to pulmonary and infectious disease specialists and consider bronchoscopy or BAL.Initiate treatment with 1-2 mg/kg/day oral prednisone or equivalent.If event resolves to Grade 1 or better, resume atezolizumab.^bIf event does not resolve to Grade 1 or better while withholding atezolizumab, permanently discontinue atezolizumab and contact Sponsor.^c
Pulmonary event, Grade 3 or Grade 4	
Permanently discontinue atezolizumab and contact the Sponsor.^cBronchoscopy or BAL is recommended.Initiate treatment with 1-2 mg/kg/day oral prednisone or equivalent.If event does not improve within 48 hours after initiating corticosteroids, consider adding an immunosuppressive agent.If event resolves to Grade 1 or better, taper corticosteroids over ≥ 1 month.

BAL=bronchoscopic alveolar lavage; IVIG=intravenous immunoglobulin

a. Atezolizumab may be withheld for a longer period of time (ie, >12 weeks after event onset) to allow for corticosteroids (if initiated) to be reduced to ≤ 10 mg/day oral prednisone or equivalent. The acceptable length of the extended period of time must be agreed upon by the investigator and the Sponsor.

b. If corticosteroids have been initiated, they must be tapered over ≥ 1 month to ≤ 10 mg/day oral prednisone or equivalent before atezolizumab can be resumed.

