11.6.2.4 Endocrine Events

Thyroid disorders, type 1 diabetes mellitus, adrenal insufficiency, and pituitary disorders have been associated with the administration of atezolizumab.

Subjects with unexplained symptoms such as fatigue, myalgias, impotence, constipation, or mental status changes, should be investigated for the presence of thyroid, pituitary, or adrenal endocrinopathies. An endocrinologist should be consulted if an endocrinopathy is suspected. Thyroid stimulating hormone (TSH), triiodothyronine 3 (T3), and free thyroxine (T4) levels should be obtained to determine whether thyroid abnormalities are present. Pituitary hormone levels and function tests (e.g., TSH, growth hormone, luteinizing hormone, follicle-stimulating hormone, testosterone, prolactin, adrenocorticotrophic hormone [ACTH] levels and ACTH stimulation test) and MRI of the brain (with detailed pituitary sections) may help to differentiate primary adrenal insufficiency from primary pituitary insufficiency.

For specific management guidelines, please see Table 6.

Table 6. Management Guidelines for Endocrine Events

Adverse Event	Management
Asymptomatic hypothyroidism	
▪ Continue atezolizumab.▪ Initiate treatment with thyroid replacement hormone.▪ Monitor TSH weekly.
Symptomatic	
▪ Withhold atezolizumab.▪ Initiate treatment with thyroid replacement hormone.

Adverse Event	Management
hypothyroidism	
Monitor TSH weekly.Consider subject referral to endocrinologist.Resume atezolizumab when symptoms are controlled and thyroid function is improving.
Asymptomatic hyperthyroidism	
TSH \geq0.1 mU/L and $<$0.5 mU/L:
 
Continue atezolizumab.Monitor TSH every 4 weeks. 
TSH $<$0.1 mU/L:
 
Follow guidelines for symptomatic hyperthyroidism.
Symptomatic hyperthyroidism	
Withhold atezolizumab.Initiate treatment with anti-thyroid drug such as methimazole or carbimazole as needed.Consider subject referral to endocrinologist.Resume atezolizumab when symptoms are controlled and thyroid function is improving.Permanently discontinue atezolizumab and contact the Sponsor for life-threatening immune-related hyperthyroidism.^a

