11.6.2.7 Pancreatic Events

Symptoms of abdominal pain associated with elevations of amylase and lipase, suggestive of pancreatitis, have been associated with the administration of atezolizumab. The differential diagnosis of acute abdominal pain should include pancreatitis. Appropriate work-up should

include an evaluation for ductal obstruction, as well as serum amylase and lipase tests. For specific management guidelines please see Table 9.

Table 9. Management Guidelines for Pancreatic Events, Including Pancreatitis

Adverse Event	Management
Amylase and/or lipase elevation, Grade 2	
▪ Continue atezolizumab.▪ Monitor amylase and lipase weekly.▪ For prolonged elevation (e.g., >3 weeks), consider treatment with 10 mg/day oral prednisone or equivalent.
Amylase and/or lipase elevation, Grade 3 or 4	
▪ Withhold atezolizumab for up to 12 weeks after event onset.^a▪ Refer subject to gastrointestinal specialist.▪ Monitor amylase and lipase every other day.▪ If no improvement, consider treatment with 1-2 mg/kg/day oral prednisone or equivalent.▪ If event resolves to Grade 1 or better, resume atezolizumab.^b▪ If event does not resolve to Grade 1 or better while withholding atezolizumab, permanently discontinue atezolizumab and contact Sponsor.^c▪ For recurrent events, permanently discontinue atezolizumab and contact the Sponsor.^c
Immune-related pancreatitis, Grade 2 or 3	
▪ Withhold atezolizumab for up to 12 weeks after event onset.^a▪ Refer subject to gastrointestinal specialist.▪ Initiate treatment with 1-2 mg/kg/day intravenous methylprednisolone or equivalent and convert to 1-2 mg/kg/day oral prednisone or equivalent upon improvement.▪ If event resolves to Grade 1 or better, resume atezolizumab.^b▪ If event does not resolve to Grade 1 or better while withholding atezolizumab, permanently discontinue atezolizumab and contact Sponsor.^c▪ For recurrent events, permanently discontinue atezolizumab and contact the Sponsor.^c

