11.6.2.9 Neurologic Disorders

Myasthenia gravis, Guillain-Barré syndrome, and meningoencephalitis have been observed with single agent atezolizumab. Subjects may present with signs and symptoms of sensory or motor neuropathy. Diagnostic work-up is essential for an accurate characterization to differentiate between alternate etiologies. For specific management guidelines please see Table 11.

Table 11. Management Guidelines for Neurologic Disorders, Including Meningoencephalitis

Adverse Event	Management
Immune-related neuropathy, Grade 1	
Continue atezolizumab.Investigate etiology.
Immune-related neuropathy, Grade 2	
Withhold atezolizumab for up to 12 weeks after event onset.^aInvestigate etiology.Initiate treatment as per institutional guidelines.If event resolves to Grade 1 or better, resume atezolizumab.^bIf event does not resolve to Grade 1 or better while withholding atezolizumab, permanently discontinue atezolizumab and contact the sponsor
Immune-related neuropathy, Grade 3 or 4	
Permanently discontinue atezolizumab and contact the Sponsor.^cInitiate treatment as per institutional guidelines.

Adverse Event	Management
Myasthenia gravis and Guillain-Barré syndrome (any grade)	
▪ Permanently discontinue atezolizumab and contact the Sponsor.^c▪ Refer subject to neurologist.▪ Initiate treatment as per institutional guidelines.▪ Consider initiation of 1-2 mg/kg/day oral or IV prednisone or equivalent.
Immune-related meningoencephalitis, all grades	
▪ Permanently discontinue atezolizumab and contact the Sponsor.^c▪ Refer subject to neurologist.▪ Initiate treatment with 1-2 mg/kg/day IV methylprednisolone or equivalent and convert to 1-2 mg/kg/day oral prednisone or equivalent upon improvement.▪ If event does not improve within 48 hours after initiating corticosteroids, consider adding an immunosuppressive agent.▪ If event resolves to Grade 1 or better, taper corticosteroids over ≥ 1 month.

IV=intravenous

- a. Atezolizumab may be withheld for a longer period of time (ie, >12 weeks after event onset) to allow for corticosteroids (if initiated) to be reduced to ≤ 10 mg/day oral prednisone or equivalent. The acceptable length of the extended period of time must be agreed upon by the investigator and the Sponsor.

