13.9.1 Adverse Event of Special Interest

AESIs require ongoing monitoring by investigators and rapid identification and communication by the investigator to the sponsor. All AESIs, whether they are SAEs or not, must be reported immediately (within 24 hours) to the sponsor. The sponsor has determined that the events listed below (whether considered serious or non-serious by investigators) should be considered AESIs, and should therefore be reported within 24 hours:

- 1) In relation to bosutinib:
 - A. Grade 3-4 diarrhea
 - B. Grade 3-4 nausea and vomiting
 - C. Potential drug-induced liver injury showed by abnormal values in liver enzyme (ALT increased and AST increased) concurrent with abnormal elevation in total bilirubin that meet the criteria outlined below:
 - a. Patients with AST or ALT and total bilirubin baseline values within the normal range who subsequently present with AST or ALT ≥ 3 times the upper limit of normal concurrent with a total bilirubin $\geq 2 \times$ ULN with no evidence of hemolysis and an alkaline phosphatase $\leq 2 \times$ ULN or not available;
 - b. For patients with preexisting ALT or AST or total bilirubin values above the upper limit of normal, the following threshold values should be used:
 - i. For patients with pre-existing AST or ALT baseline values above the normal range: AST or ALT ≥ 2 times the baseline values and $\geq 3 \times$ ULN, or $\geq 8 \times$ ULN (whichever is smaller).
 - ii. For patients with pre-existing values of total bilirubin above the normal range: Total bilirubin increased by one time the upper limit of normal or ≥ 3 times the upper limit of normal (whichever is smaller).

D. Myelosuppression (Anemia, Neutropenia, Leukopenia) considered clinically significant by the investigator.

E. Hemorrhage considered clinically significant by the investigator

F. Infection

G. Skin disorders (Rash) considered clinically significant by the investigator

H. Clinically significant immunological events (Hypersensitivity)

I. Renal dysfunction (increased blood creatinine considered clinically significant by the investigator)

J. Pleural effusions

K. Clinically significant cardiac events (QT prolongation, atrial fibrillation, sinus bradycardia, tachycardia, supraventricular tachycardia, bradycardia, premature ventricular contractions, pericardial effusion, right bundle branch block, sinus tachycardia, or premature atrial contractions).

2) In relation to atezolizumab:

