- A. Cases of potential drug-induced liver injury that include an elevated ALT or AST in combination with either an elevated bilirubin or clinical jaundice, as defined by Hy's Law (see *EASL, 2019*)
- B. Suspected transmission of an infectious agent by the study treatment, as defined below
 - Any organism, virus, or infectious particle (e.g., prion protein transmitting transmissible spongiform encephalopathy), pathogenic or non-pathogenic, is considered an infectious agent. A transmission of an infectious agent may be suspected from clinical symptoms or laboratory findings that indicate an infection in a patient exposed to a medicinal product. This term applies only when a contamination of study treatment is suspected.

C. Systemic lupus erythematosus

D. Events suggestive of hypersensitivity, infusion-related reactions, cytokine-release syndrome, macrophage activating syndrome, hemophagocytic lymphohistiocytosis

E. Nephritis

F. Ocular toxicities (e.g., uveitis, retinitis, optic neuritis)

G. Grade ≥ 2 cardiac disorders (e.g., atrial fibrillation, myocarditis, pericarditis)

H. Vasculitis

I. Autoimmune hemolytic anemia

J. Severe cutaneous reactions (e.g., Stevens-Johnson syndrome, dermatitis bullous, toxic epidermal necrolysis)

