15.3.2 Adverse Events

Summary tables for adverse events (AEs) have to include only AEs that started or worsened during the on-treatment period, the treatment-emergent AEs (TEAEs). However, all safety data (including those from the pre-treatment period) will be listed and those collected during the pre-treatment period are to be flagged.

The incidence of treatment-emergent adverse events (new or worsening from baseline) will be summarized by system organ class and/or preferred term, severity (based on CTCAE grades), type of adverse event, causality relation to study treatment by the phases or subsets previously described.

Deaths reportable as SAEs and non-fatal serious adverse events will be listed by patient and tabulated by type of adverse event and safety subset.

Specific safety event categories will be considered. Such categories consist of one or more well-defined safety events which are similar in nature and for which there is a specific clinical interest in connection with the study treatment(s).

For each specified safety event category, number and percentage of patients with at least one event part of the safety set will be reported. Also AESI will be summarized and analyzed.

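### The closed AESI list in Protocol 13.9.1 has no entry for four toxicity groups that Section 11.6.2 attributes to atezolizumab, so cases judged non-serious fall outside 24-hour reporting and are not named in the AESI summary

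*Protocol*

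**What the plan says.** Protocol 13.9.1 fixes the list by enumeration: "The sponsor has determined that the events listed below (whether considered serious or non-serious by investigators) should be considered AESIs". Bosutinib has eleven entries (A-K) and atezolizumab ten (A-J). Neither part ends with an open item. Being on the list has a direct consequence: "All AESIs, whether they are SAEs or not, must be reported immediately (within 24 hours) to the sponsor". It also decides what enters a planned summary, since Protocol 15.3.2 says "Also AESI will be summarized and analyzed".

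Section 11.6.2 describes the toxicities of atezolizumab, most with a management table. On the groups at issue it says:

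- 11.6.2.1: "Dyspnea, cough, fatigue, hypoxia, pneumonitis, and pulmonary infiltrates have been associated with the administration of atezolizumab"
- 11.6.2.4: "Thyroid disorders, type 1 diabetes mellitus, adrenal insufficiency, and pituitary disorders have been associated with the administration of atezolizumab"
- 11.6.2.7, on abdominal pain with raised amylase and lipase: "suggestive of pancreatitis, have been associated with the administration of atezolizumab"
- 11.6.2.9: "Myasthenia gravis, Guillain-Barré syndrome, and meningoencephalitis have been observed with single agent atezolizumab"

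Section 11.6.2.10 adds that immune-related meningoencephalitis is an identified risk, and 11.6.2.3 links immune-mediated colitis to the drug.

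SAP 6.9 repeats that AESIs will be summarized, but its table of safety data gives a different AESI list: seven vascular events, then an eighth item for anything else the investigator considers important.

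**The concern.** The primary objective is the safety of bosutinib combined with atezolizumab. AESI status puts an event of known interest on the 24-hour path without depending on a judgment of seriousness, and it groups such events in one summary. If the list omits immune toxicities that the same protocol attributes to the drug, neither function works for them.

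No stated rule explains the selection. The atezolizumab part includes lupus, vasculitis and autoimmune hemolytic anemia, none of which has a subsection in 11.6.2. The bosutinib part includes infection with no grade or significance qualifier. Nephritis and Grade 2 or higher cardiac disorders are listed; pneumonitis and hypophysitis are not.

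**Working it through.** The plan gives no figure to reproduce. The check is a comparison of 11.6.2 with 13.9.1.

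**Number of groups.** Section 11.6.2 has 13 subsections (11.6.2.1 to 11.6.2.13). Neurologic disorders (11.6.2.9) and meningoencephalitis (11.6.2.10) share Table 11, so they are one group: 13 − 1 = 12. The tables give the same count: Tables 3 to 13 are 11 tables, and the infusion-reaction table makes 12.

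**Mapping to 13.9.1.**

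| Group in 11.6.2 | Entry in 13.9.1 | Coverage |
|---|---|---|
| Pulmonary | none | none |
| Endocrine | none | none |
| Pancreatic | none | none |
| Neurologic incl. meningoencephalitis | none | none |
| Gastrointestinal/colitis | bosutinib A, Grade 3-4 diarrhea | indirect |
| Hepatic | atezolizumab A; bosutinib C | only with raised bilirubin or jaundice |
| Myocarditis | atezolizumab G | Grade 2 or higher |
| Dermatologic | atezolizumab J; bosutinib G | severe, or clinically significant rash |
| Ocular | atezolizumab F | yes |
| Nephritis | atezolizumab E | yes |
| Systemic immune activation | atezolizumab D | yes |
| Infusion-related reactions | atezolizumab D | yes |

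Totals: 4 not covered + 1 indirect + 3 above a threshold + 4 covered = 12. Not covered: 4/12 = 33%.

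The nearest bosutinib entries do not close the gap. Pleural effusions and infection are different events. Entry H, on clinically significant immunological events, is qualified in brackets as hypersensitivity.

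**One case followed through the rules.** Take a Grade 2 pneumonitis on D60 in a Group 1 patient, treated as an outpatient. D60 lies in Cycle 3 (which starts on D57), within the two combination cycles at 840 mg every two weeks.

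1. *DLT (9.3.1)?* No. The non-hematological criteria require Grade 3 or higher.
2. *SAE (13.8)?* Only if the investigator judges it medically significant; there is no hospitalization or immediate threat to life.
3. *AESI (13.9.1)?* No entry.
4. *Sponsor contact (Table 3)?* Atezolizumab is withheld for up to 12 weeks and oral corticosteroids start. Sponsor contact is called for only if the event does not resolve to Grade 1, or if a longer hold has to be agreed.

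By contrast, Grade 2 myocarditis and Grade 2 nephritis call for sponsor contact at once (Tables 8 and 12), and both are AESIs.

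**The SAP list.** None of the four groups, nor colitis, is among the seven named items in SAP 6.9. Only item 8 could admit them, case by case. Correcting 13.9.1 alone would therefore not change the AESI table, and copying 13.9.1 unchanged into the SAP would carry the omission over.

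**The case against.** The strongest case on the other side is that little is lost, and several of its points stand.

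- A reader might infer that 24-hour reporting misses major immune toxicities. The documents do not support that. Section 13.4 puts every SAE on the same 24-hour path, and 13.8 and 13.9 count medically important events as serious even without hospitalization. Only cases judged non-serious fall through.
- A reader might infer that the 10-patient DLT stage is compromised. It is not. DLTs are defined independently of AESI status, and the rule of 2 or more patients does not use the list.
- A reader might infer that events drop out of the primary analysis. They do not. Protocol 15.3.2 tabulates all treatment-emergent events by system organ class and/or preferred term, grade, causality and phase. Amylase and lipase are measured during combination treatment and fall under the laboratory summaries of 15.3.3.
- A reader might count 5 of 13 groups as missing. That counts meningoencephalitis twice.
- A reader might conclude that such a pneumonitis would certainly be absent from the AESI table. Item 8 in SAP 6.9 could admit it.
- Some omitted events reach the sponsor by another route. Myasthenia gravis of any grade requires sponsor contact under Table 11, though with no 24-hour limit.
- The protocol nowhere says that the AESI list must mirror the management sections; its scope is the sponsor's decision.

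These points bound the consequence without removing it. For cases judged non-serious, prompt reporting rests on the judgment that AESI status is meant to bypass. The general tables spread immune events over many rows, and the specific safety event categories in 15.3.2 that might group them are never listed. No reason is given for leaving the four groups out.

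**Conclusion.** The omission is real and its effect is limited. Four of the 12 toxicity groups in 11.6.2 (33%) have no AESI entry under either drug, and colitis is reached only as Grade 3-4 diarrhea under bosutinib. The loss has two parts: (a) no 24-hour report for cases judged non-serious, and (b) no named place in the AESI summary, where the separate SAP list leaves inclusion to an open item. Serious cases, the DLT rule and the general adverse event tables are unaffected.

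This rests on reading 13.9.1 as closed and bosutinib entry H as hypersensitivity only. The 33% counts toxicity groups, not patients. The documents give no expected frequency for non-serious cases, so the number of affected reports cannot be estimated. The change is worth making because it is cheap and safety is the primary objective.

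**What to change.** Reconcile Protocol 11.6.2, Protocol 13.9.1 and SAP 6.9 into one AESI list.

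1. Add to 13.9.1 part 2: pneumonitis, colitis, endocrinopathies, pancreatitis, and neurologic disorders including meningoencephalitis. If a group is left out on purpose, state why.
2. Have the sponsor set a grade or clinical-significance threshold for each, as several existing entries do. Without one, events such as asymptomatic hypothyroidism, for which Table 6 continues atezolizumab, would each need a 24-hour report.
3. Use the completed list for the AESI table in SAP 6.9, so that the same list drives reporting and analysis.

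The cost is wording in the protocol, SAP and eCRF, and a few more 24-hour reports in a trial of 36 patients; how many depends on the thresholds. No dose or management rule changes.

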13.10 Information to Be Provided by the Investigator for a SAE or AESI

The following information about the patient and the event must be provided to the sponsor:

- Investigator identification,

- Patient identification (e.g., sex, age, date of birth, code),
- Information on study drug (e.g., start/stop date, dose and frequency of study drug administered),
- Description of event.

In addition to the above information, the sponsor will require the investigator's assessment of the following:

- Severity of the SAE or AESI,
- Relationship of the SAE or AESI to the study drug,
- Outcome of the SAE or AESI.

13.11 Follow-up Information on a SAE or AESI

Appropriate diagnostic tests should be performed and therapeutic measures, as medically indicated, should be instituted. Appropriate consultation and follow-up evaluations should be carried out until the event has resolved or is otherwise explained by the investigator. For all SAEs or AESIs, the investigator must pursue and provide information to the sponsor. In addition, an investigator may be requested by the sponsor to obtain specific information in an expedited manner. This information may be more detailed than that captured on the AE form.

In general, this information will include a description of the AE, provided in sufficient detail to allow for a complete medical assessment of the case and independent determination of possible causality. Information on other possible causes, such as concomitant medication and illnesses, must also be provided.

13.12 Required Follow-up for SAEs or AESIs

Routine follow-up should be conducted through and including 28 days after the last administration of assigned study treatment in the trial or the investigator/patient decision to discontinue treatment, whichever occurs later, in all patients, in order to monitor the occurrence of SAEs or AESIs. After this time, ongoing AEs thought to be at least possibly study-drug related, as well as all ongoing SAEs, should be followed at least every 4 weeks until they resolve to baseline (or to NCI CTCAE, v5.0 grade ≤ 1), stabilize, or are considered to be chronic/irreversible. The medical monitor may specify a longer follow-up period if required to assure the safety of the patient.

